Тур	e: 🗆 Home 🗆 Mobile 🗆 Work	□ Other	
c. Alternate Mailir	ng Address		
	Address Line 1		
	Address Line O		
	Address Line 2		
	City	State	Zip
15. Relationship to p	patient?		
	 □ Spouse (husband or wife) □ Sibling □ Son or daughter □ Friend or neighbor □ Parent or legal guardian □ Other, specify: 		
D DEMOCRAPHIC	S AND IN-HOSPITAL DATA		

☐ Asian☐ American☐ Native HI): rican American Indian / Alaska Native / Other Pacific Islander	
18. Hispanic ethnicity: ☐ Yes	□ No	
☐ Medicare	Supplemental Insurance / Med surance npus / other	ligap
20. Does the patient have documented	ed past medical history of the f	ollowing (check all that apply):
☐ Stroke☐ Transient ischemic attack	☐ Hypertension☐ Dyslipidemia	☐ Chronic renal insufficiency☐ Heart Valve☐ Current pregnancy or within 6
 □ Atrial Fibrillation or Flutter □ Myocardial infarction or CAD □ Congestive heart failure □ Carotid stenosis □ Peripheral arterial disease 	 ☐ Smoking ☐ Depression ☐ Drug/alcohol abuse ☐ Family history of stroke ☐ Migraines 	weeks post-partum Hormone replacement therapy Sickle cell Sleep apnea Diabetes mellitus
21. Please enter the body mass inde	x (BMI) kg/m²	□ Not documented
22. What was the patient's ambulator	ry status prior to admission ?	
		vithout a device)
23. Initial NIH Stroke Scale Score (00)-42)	Not documented
25. Did the initial exam show aphasia	a? ☐ Yes ☐ No / not do	ocumented
26. Hospital admission date for this e	event: / /	/
☐ No admission date; patient was	not admitted as an inpatient (s	select reason below)
	lirectly from ED to home rom observation status without	inpatient admission

2/a. If YES	S, check all that apply:	
☐ Hom	e health Physical Therapy e health Occupational Therapy e health Speech Therapy Outpatient Physical Therapy Outpatient Occupational Therapy Outpatient Speech Therapy	
27b. If NO	indicate why not	
☐ Patie	nt not evaluated for need of rehab services nt not in need of rehab services nt / family refused r reason	
28. What w	as the patient's ambulatory status at discharge?	
	 □ Able to ambulate independently (with or without a device) □ With assistance (from person) □ Unable to ambulate □ Not documented 	
30. Hospita	I discharge date:	
	ollow-up clinic visit with a nurse, nurse practitioner, or physician assistant (i.e. p nal care clinic, neurologist, or other doctor visit) scheduled prior to discharge?	rimary care,
	☐ Yes → Fill in type and date below	
31a	☐ No If YES, check all visit types that apply and enter the date (if known)	
0.4	□ Primary care	
	COMPASS clinic visit	
	Other transitional care visit with nurse and APP	
	☐ Other transitional care visit with primary care	I ·
	□ Rehab	
	□ Neurologist	
	□ Cardiologist	
	□ Other	
32. Name o	f patient's primary care provider:	_ □ Not known

ppnemier resources	
34. Did the PAC notify the patient of the COMPASS study by distributing the brochure?	
 ☐ Yes, distributed the brochure in person ☐ Yes, mailed brochure to patient ☐ No Fill in date below Fill in date below	
If YES, enter date of notification or mailing:	
Month Day Year	
END OF PARTICIPANT ENROLLMENT FORM	
Participant Enrollment Form v2.0 for Phase 2	Page 5 of 5

Appendix 39 - Consent Matrix

MEMORANDUM

To: Wake Forest Health Sciences IRB

From: [name], MSPH

Date: May 12, 2016

Subject: Outlines how data from COMPASS will be used for research purposes

The COMPASS Study is enrolling all eligible patients from participating hospitals. All patients are informed about the study and they are enrolled. This is done prior to gaining explicit consent from the patient. This is permissible because of the low-risk nature of the study and meeting the criteria for HIPAA Waivers.

Recognizing that this process is novel and different from other traditional approaches to consent, the study team worked through a number of scenarios to better define who is included in research analysis and who is excluded. That is detailed in the consent matrix on the next page.

Like all other studies, COMPASS patients can opt out (or withdraw) from the study at any time. At four time points COMPASS letters are provided to each enrolled patient and each letter includes information on how they can opt-out from the study (a brochure, 30d letter, 60d letter, & 80d letter).

In determining what data were acceptable to use for analysis, our team considered both the regulatory requirements and additional protections to conservatively maintain the rights and welfare of study participants. In particular, we determined that we would not use any data past the eligibility screening form from patients who withdrew from the study regardless of the time point of withdrawl. This is more stringent from the regulation, which says that studies can use data up until the point that a patient withdraws. However, since COMPASS is not explicitly gaining consent prior to enrollment (instead we are relying on the patient to out-out) we will make the assumption that if someone was to opt-out (i.e. withdraw) that same patient would not have initially provided consent to be enrolled.

In addition, if a patient withdrawals from the study (again at any time point) that withdrawal will also remove that patient's clinical data from research analysis, even if that patient had provided signed clinical consent (at the 7-14 day visit). This was put in place because the study team made the conservative estimate that a study patient would not be able to adequately distinguish between the two consent processes and articulate their wish to withdraw from some but all parts of the study.

Data Usage for Research Purposes

Data Form	Covered by	Rules for Use	Exclusions from Analysis
ELG	Limited HIPAA waiver	All patients (includes patients who withdrew).	
ENR	Full HIPAA waiver	All patients, except any patients who withdrew from the study (at any time point).	Withdraw=1
NCSCC	Full HIPAA waiver	All patients, except any patients who withdrew from the study (at any time point).	Withdraw=1
2-d call	eCare consent	Include all patients who provided signed "clinic consent" and who have not withdrawn.	Research_consent ^=1 withdraw =1
Clinic forms	eCare consent	Include all patients who provided signed "clinic consent" and who have not withdrawn.	Research_consent ^=1 withdraw =1
eCare Plan	eCare consent	Include all patients who provided signed "clinic consent" and who have not withdrawn.	Research_consent ^=1 withdraw =1
30-d Call	eCare consent	Include all patients who provided signed "clinic consent" and who have not withdrawn.	Research_consent ^=1 withdraw =1
60-d Call	eCare consent	Include all patients who provided signed "clinic consent" and who have not withdrawn.	Research_consent ^=1 withdraw =1
90-d Data	90-d verbal consent	All patients, except any patients who withdrew from the study (at any time point).	Withdraw=1
Claims data	Full HIPAA waiver	We have a HIPAA Waiver to collect claims data on all patients. The data that we are using to link is from the COMPASS Dataset. Here is our linkage plan: • ELG form: We will use patient data from all records even if they withdrew from the study. • ENR form: We will use patient data to link them as long as they have not withdrawn from the study (at any time point).	
2-d Dispo	Full HIPAA waiver	All patients, except any patients who withdrew from the study (at any time point).	Withdraw=1
Clinic Dispo	Full HIPAA waiver	All patients, except any patients who withdrew from the study (at any time point).	Withdraw=1

March 19, 2021 Application - IRB00035998

1 LIST OF ABBREVIATIONS

Term	Abbreviation
Agency for Healthcare Research and Quality	AHRQ
Blue Cross & Blue Shield of North Carolina	BCBSNC
Centers for Medicare & Medicaid Services	CMS
Current Procedural Terminology	СРТ
Emergency department	ED
Healthcare Common Procedure Coding System	HCPCS
International Classification of Diseases	ICD
Inpatient rehabilitation facility	IRF
Post-acute care	PAC
Skilled nursing facility	SNF
Transient ischemic attack	TIA
Transitional care management	ТСМ
Usual care	UC

2 CLAIMS STATISTICAL ANALYSIS ADDENDUM OBJECTIVES

The objective of the COMPASS Study as it pertains to this addendum is to evaluate the comparative effectiveness of the COMPASS Intervention compared to usual care (UC) with respect to a collection of claims-based outcomes and mortality. The COMPASS Study design is described in the Phase 1 Statistical Analysis Plan, available at https://clinicaltrials.gov/ct2/show/NCT02588664.

3 ADMINISTRATIVE DATA SOURCES & LINKAGE

3.1 Data Sources

Administrative claims data will be used to examine the following secondary endpoints: 1) hospital readmissions, 2) emergency department visits, 3) skilled nursing and inpatient rehabilitation facility admissions, 4) ambulatory care visits, and 5) transitional care management services. Patients' longitudinal claims data for inpatient and ambulatory care services utilized in the year after index discharge will be obtained for Centers for Medicare and Medicaid Services (CMS) Medicare fee-for-service, State Medicaid, and Blue Cross Blue Shield of North Carolina (BCBSNC) beneficiaries residing in North Carolina.

Administrative data will be obtained from the Centers for Medicare and Medicaid Services (Medicare), the Division of Medical Assistance, NC Department of Health and Human Services (Medicaid), and the BCBSNC. Claims from each of the insurance providers contain several component datasets. Each payer's data include a beneficiary summary or enrollment file, which captures each patient's demographic and enrollment information. Additional datasets containing the claims provide detailed information on inpatient and outpatient healthcare utilization. The healthcare utilization file structure and organization vary by insurance provider (e.g., Medicare, BCBSNC). Files are broadly categorized under: Inpatient; Outpatient; Physician; Prescription drugs; Medical equipment; post-acute care (e.g., skilled nursing facility, home health); and hospice or end-of-life-care services. The administrative claims will be obtained through data reuse agreements and direct data purchase.

When harmonized, these claims files will allow us to ascertain details about healthcare service utilization, including diagnoses and procedures for which an insurance claim was filed. The analytical file will be organized at the beneficiary level, with multiple observations reflecting relevant healthcare encounters. Primary and comorbid diagnoses will be identified using the International Classification of Disease Diagnosis Group coding, version 10 (ICD-10-CM diagnoses). Diagnostic discharge codes will also be grouped into clinically meaningful categories using the Clinical Classification Software.¹ Healthcare procedure and service utilization will be defined from the Healthcare Common Procedure Coding System, including Current Procedural Terminology codes and ICD-10-CM procedure codes.

Combining the codes from all relevant insurance claims files will enable us to observe patients before and during the hospital encounter, and in post-discharge follow-up. Service utilization and outcomes can be observed within the claims files as long as the patient maintains continuous insurance coverage and an insurance claim is filed for the event.

3.2 Linkage Methodology

Given that the claims may not include direct patient identifiers that can be merged with study data, we need to develop a linkage methodology. We will document the proportion of records that were successfully linked by data source. Following is a description of the proposed methodology for each data source.

Medicare. The Medicare Master beneficiary Summary File will be linked with COMPASS patient data using iterative deterministic linkage protocols. Linkage variables will include: gender, date of birth, index discharge hospital, and date of discharge/dates of service. Dates will be allowed to match within +/- 3 days or on 2 of 3 date elements (day, month, and year). Such fuzzy matches will be reviewed and verified the presence of stroke-related ICD10 diagnostic codes in the claims and comparisons of Zip code information between COMPASS records and Medicare enrollment data.

BCBSNC. The BCBSNC claims will be linked with the COMPASS data using an iterative deterministic linkage protocol. Linkage variables will include patients' first name, middle name (initial) and last name, as well as patients' date of birth and gender. Manual review of matches will be conducted by two independent reviewers with discrepancies adjudicated by a third reviewer. Review of the possible linkages will include comparison of service dates (e.g., discharge date) and patient addresses available from the BCBS NC claims and the COMPASS data.

Medicaid. The North Carolina Department of Health and Human Services, as the custodian of the state Medicaid data, will perform the linkage of those data with COMPASS patient data, using as linkage variables patients' first name, middle name (initial) last name, date of birth and sex.

Mortality. COMPASS data will be linked to the North Carolina mortality data for the years 2016-2020 to obtain information on death up to 1 year following the index hospitalization discharge. A deterministic linkage of the mortality data with COMPASS data will be performed using name, address, sex, and date of birth as the identifier variables. Two independent reviewers will determine the matches and a third person will adjudicate differences.

4 ENDPOINTS

Table 1 describes the set of outcomes and associated endpoints to be analyzed as a part of the claims analyses described in this statistical analysis plan. For each outcome, the data source, endpoint, reference period for which the endpoint is defined, and estimand are provided. For ITT analyses, the estimand defines a comparison between the COMPASS Intervention arm and the UC arm.

Table 1. Endpoints for Claims and Mortality Analysis				
Source	Outcome	Endpoint	Reference Period	Estimand
Claims	All Cause Hospital Readmissions	Incidence	30-days post index hospitalization discharge (unplanned)	Odds Ratio
		Incidence	90-days post index hospitalization discharge (unplanned)	Odds Ratio
		Time-to-hospital readmission	1-year post index hospitalization discharge	Hazard Ratio from recurrent events model
	Recurrent Stroke Hospital Readmissions	Time-to-recurrent stroke	1-year post index hospitalization discharge	Hazard Ratio from recurrent events model
	Emergency Department Visits	Time-to-first emergency department visit	1-year post index hospitalization discharge	Hazard Ratio
	Admission to Skilled Nursing/Inpatient Rehab Facility	Time-to first SNF/IRF admissions	1-year post index hospitalization discharge	Hazard Ratio
	Continuity of Care	Time-to-first visit with any provider	1-year post index hospitalization discharge	Hazard Ratio
	TCM Billing	Incidence	14-days post index hospitalization discharge	Odds Ratio
Claims & Mortality Index	All-Cause Mortality	Time-to-death by any cause	1-year post index hospitalization discharge	Hazard Ratio

Specific details regarding the definition of the endpoints is given subsequently in Section 4. Details regarding the analysis populations for the Phase 1 and Phase 2 analyses is given in Section 5. Specific details on statistical analysis methodology for endpoints having a common estimand (e.g., an odds ratio) are described in Section 6 as is general statistical methodology pertinent to all analyses.

4.1 All-Cause Hospital Readmissions

The primary readmission endpoint is defined as incidence of readmission (as an inpatient or under observation status) to a non-federal, acute care hospital for any unplanned reason within 90 days of discharge from the index stroke event. Reasons for hospital readmission will be

defined using the principal ICD-10-CM diagnostic code from the associated claim. Planned readmissions will be defined as a hospital readmission for a scheduled procedure for which acute stroke is not also listed as the primary discharge diagnosis code (suggesting the readmission was due to recurrent stroke) and will be excluded.² The following procedures will be considered as planned following the index stroke hospitalization: carotid endarterectomy, carotid stenting, percutaneous carotid stenting, intracranial and intervertebral stenting, patent foramen ovale closure, ablation, aortic or mitral valve replacement and cranioplasty. All planned procedures will be identified by ICD-10 procedure codes. Observation stays will be identified from outpatient (Medicare) and facility (Medicaid and BCBSNC) claims using the G0378 and G0379 Healthcare Common Procedure Coding System (HCPCS) codes.

We will also analyze two secondary all-cause readmission endpoints. The first, unplanned readmissions within 30 days of discharge from the index stroke hospitalization will be defined analogously to the primary readmissions endpoint. The other secondary readmission endpoint will be defined as the hazard ratio from a recurrent time-to-event analysis over the 12 month period following discharge from the index stroke hospitalization. Planned readmissions will not be excluded from the recurrent time-to-event analysis.

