4.2 Emergency Department Visits

The ED visits endpoint will be defined as the time to first ED visit with the associated estimand being the hazard ratio from a recurrent time-to-event analysis. Emergency department visits will be identified from Medicare Outpatient claims files using the HCPCS codes for evaluation and management of a patient seen in the ED without further admission to the hospital (HCPCS codes: 99281-99285) and from the MedPAR (year 2016) and Inpatient files (years 2017-2019) as claims with revenue center codes 0450-0459, 0981 or a hospital inpatient claim with an emergency room charge>\$0. Emergency department visits will be identified from CMS Medicaid Professional claims with revenue service codes 99281-99285. ED visits will be identified from the BCBS Professional and Facility claims with place of service code=23 and the following revenue service codes: 0450', '0451', '0452', '0456', '0459', '0981','450', '451', '452', '456', '459', '981','00450', '00451', '00452', '00456', '00459', '00981'. Patients will be administratively censored one year after index hospitalization discharge.

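### SAP 4.1 gives no test for whether a readmission was scheduled, so emergency readmissions without acute stroke as primary diagnosis that end in a listed procedure drop out of the 30- and 90-day unplanned endpoints

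*SAP*

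**What the plan says.** SAP 4.1 makes the 90-day outcome its primary readmission endpoint: readmission "for any unplanned reason within 90 days of discharge from the index stroke event". The 30-day endpoint follows the same rule: "unplanned readmissions within 30 days of discharge from the index stroke hospitalization will be defined analogously to the primary readmissions endpoint". SAP Table 1 labels both as unplanned.

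In concept, a planned readmission is "a hospital readmission for a scheduled procedure for which acute stroke is not also listed as the primary discharge diagnosis code", and it is excluded. The SAP then turns the concept into a list: "The following procedures will be considered as planned following the index stroke hospitalization: carotid endarterectomy, carotid stenting, percutaneous carotid stenting", followed by intracranial and intervertebral stenting, patent foramen ovale closure, ablation, aortic or mitral valve replacement, and cranioplasty. The means of finding them is given in one sentence: "All planned procedures will be identified by ICD-10 procedure codes".

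SAP 4.1 names no admission type, admission source or emergency marker. It treats the 1-year analysis differently: "Planned readmissions will not be excluded from the recurrent time-to-event analysis".

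SAP 4.2 already identifies emergency care on Medicare inpatient files through "claims with revenue center codes 0450-0459, 0981 or a hospital inpatient claim with an emergency room charge" above zero, and gives separate identifiers for BCBSNC and Medicaid. It uses them only for the emergency department (ED) visit endpoint.

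**The concern.** The concept depends on the word *scheduled*, and nothing in the operational rule measures it. A procedure code shows that a procedure was done during the stay. It does not show that the patient was admitted for it by arrangement. An unscheduled admission whose work-up leads to a listed procedure therefore looks the same in the data as an elective one.

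The exception for acute stroke rescues some of these stays but not those with a cardiac diagnosis. Whether it rescues TIA depends on a definition that SAP 4.1 does not give. That matters because TIA is a qualifying diagnosis for the trial, an adjustment covariate (SAP 6.1) and a subgroup factor (SAP 6.5).

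At stake is the validity of the endpoint that SAP 4.1 ranks first among the readmission outcomes. Patients with a true unplanned return would be scored as having none. The comparison between arms would be distorted if such losses were more common in one arm.

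**Working it through.** The SAP states no misclassification rate, power or event count for this endpoint, so there is no figure to reproduce. The check has two parts: a trace of the rule, then an illustration of size.

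**Trace of the rule in SAP 4.1**

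| Readmission | Listed procedure code | Acute stroke as primary diagnosis | Result |
|---|---|---|---|
| Emergency, acute stroke, carotid surgery | yes | yes | kept |
| Emergency, arrhythmia, ablation | yes | no | dropped as planned |
| Emergency, TIA, carotid surgery | yes | no, if SAP 4.6 and Appendix B define acute stroke | dropped as planned |
| Emergency, no listed procedure | no | either | kept |

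The TIA row needs a step of interpretation. SAP 4.1 has no stroke code list. The only one in the SAP serves the recurrent-stroke endpoint (SAP 4.6, Appendix B). It covers I60, I61, I63 and I67.89 and has no G45 code. The protocol's Eligibility Screening Form (Appendix 3) gives the G45 series, except G45.3, as its TIA code examples. Read together, these leave TIA outside acute stroke.

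**Illustration of size**

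Inputs:
- Control 90-day risk p0 = 25%. This comes from the protocol Background and describes stroke patients discharged home without post-acute care. It is not stated to count unplanned readmissions only, so it is a stand-in.
- m = share of patients with a true unplanned readmission who are lost because their only such readmission is labelled planned. The documents give no value. Assumed range: 1% to 10%.

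Formulas: observed risk = p × (1 − m); OR = [p1/(1 − p1)] / [p0/(1 − p0)].

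Patients lost per 1,000 at p0 = 25% (1,000 × 0.25 × m): 2.5 at m = 1%, 7.5 at 3%, 12.5 at 5%, 25 at 10%.

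Equal m in both arms, true risks 20% and 25% (true OR 0.75):
- m = 1%: 19.8% and 24.75%, OR = (0.198/0.802)/(0.2475/0.7525) = 0.751
- m = 3%: 19.4% and 24.25%, OR 0.752
- m = 5%: 19.0% and 23.75%, OR 0.753
- m = 10%: 18.0% and 22.5%, OR 0.756

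If the true OR is 1.00, it stays at 1.00 under equal m.

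Unequal m, true risk 25% in both arms (true OR 1.00):

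| m, intervention | m, control | Observed OR |
|---|---|---|
| 3% | 1% | (0.2425/0.7575)/(0.2475/0.7525) = 0.973 |
| 5% | 1% | 0.947 |
| 10% | 5% | 0.932 |
| 1% | 3% | 1.027 |

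**The case against.** The best reply is that the concept already limits exclusion to scheduled procedures. On this view the procedure-code sentence only says how procedures are found, and the cited source may contain a test of scheduling. That does not close the gap. The SAP says the listed procedures are to be regarded as planned and names no field that could overrule this. A test that exists only in a cited paper is not in the plan. If emergency stays were always meant to be kept, the text still has to say which field decides.

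Other parts of the reply stand and limit the point:

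- A reader might infer that procedure codes alone decide. They do not: readmissions with acute stroke as primary diagnosis stay in.
- A reader might take the loss of TIA readmissions as certain. It follows only if the code list for another endpoint is carried into SAP 4.1.
- A reader might infer that these stays vanish from the trial's results. They remain in the 1-year recurrent-event analysis, and for Medicare an inpatient claim with an emergency marker can still count in the ED endpoint.
- An emergency marker is imperfect. An urgent direct admission from clinic would still look planned, and only intervention hospitals run the COMPASS 7–14 day visit, so that error could itself differ by arm. The marker still separates the two kinds of stay better than no marker, and a sensitivity analysis can cover the remainder.

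**Conclusion.** The gap is real but narrow. It affects the 30- and 90-day binary endpoints, only for emergency readmissions without acute stroke as primary diagnosis that carry a listed procedure, and only for patients with no other qualifying readmission in the window. Readmission is a secondary outcome of the trial.

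The size is unknown from the documents and probably small. Over the assumed 1% to 10%, the observed control risk falls from 25% to between 24.75% and 22.5%, while the odds ratio barely moves if both arms lose the same share.

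A reader might go further and infer that the treatment comparison is biased. The documents do not support that. There is a plausible route to unequal losses: only intervention patients receive the two-day call with teaching on stroke signs and calling 911 (protocol Appendix 16), and the clinic visit with referrals. Nothing shows that this changes the number of emergency admissions ending in a listed procedure, or in which direction. The shifts to 0.932 or 1.027 show what unequal loss could do; they are not estimates. The case for acting is that the rule does not measure what the endpoint claims, a better one is at hand, and the sensitivity analyses in SAP 6.2 address incomplete coverage and death but not this.

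**What to change.** Three changes:

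1. In SAP 4.1, count a readmission with a listed procedure as planned only if acute stroke is not the primary discharge diagnosis **and** the stay shows no ED origin. For Medicare inpatient stays, that means no revenue center code 0450–0459 or 0981 and no emergency room charge. For BCBSNC, use the ED codes in SAP 4.2. For Medicaid and for observation stays, require no ED claim date-matched to the start of the stay. All other readmissions with a listed procedure stay in the 30- and 90-day endpoints.
2. Define acute stroke in SAP 4.1 by code list, and state whether TIA is included.
3. Add to SAP 6.2 a sensitivity analysis that counts every readmission with a listed procedure as an event. This also covers urgent direct admissions that the ED marker misses.

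The cost is a few sentences and a small addition to the claims code, mostly with identifiers that SAP 4.2 already specifies. The extra work is the date match: SAP 4.2 takes Medicaid ED visits from professional claims, and SAP 4.1 takes Medicare observation stays from outpatient claims. Reported readmission rates would rise slightly.
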